“Improving Adherence to Cognitive Rehabilitation”

NCT02481713

Document date: 09/01/2021

Study Protocol:

This is a randomized, controlled trial investigating whether adding a brief motivational interviewing intervention to a cognitive rehabilitation training program can improve program outcomes in individuals with schizophrenia spectrum disorders. Primary outcome is cognitive rehabilitation treatment adherence. We will also examine potential mediators (increases in intrinsic motivation) and moderators (baseline variables) of the effects of MI on cognitive rehabilitation outcomes.

[figure not shown]
Approximately 120 individuals with psychotic spectrum diagnoses will be recruited. Following written informed consent and baseline assessment, they will be randomized (1:1) into one of two conditions: Motivational Interview (MI) or sham Control Interview (CI). Refer to Tables 1 and 2 for study intervention components. All participants will be invited to participate in 4 months (up to 50 sessions) of computerized cognitive rehabilitation training. Computerized cognitive training task performance and intrinsic motivation for training will be assessed at the beginning of cognitive training and at the end of each month of training. An additional assessment of cognition and functional capacity will be conducted at the midpoint (end of 2 months) of the cognitive training. All participants will also receive MI or CI booster sessions at the end of the first, second, and third month of training. At the conclusion of the 4-month cognitive training period, participants will once again undergo comprehensive assessments. Please refer to Figure below for study schematic. We anticipate that length of study participation for individual participants will be approximately 5 months.

Table 1. MI Intervention Elements

MOTIVATIONAL INTERVIEW (MI) SESSIONS
Note: throughout both MI sessions, interviewer uses common MI techniques including open-ended questions, affirmations, reflections, summaries, asking permission, rolling with resistance, expressing empathy, supporting self-efficacy, etc.
MI Session 1 (~45-60 min)
Opening remarks, focus of sessions on cognitive impairments
Open-ended discussion about participant's cognitive problems and their impact
Personal feedback on neurocognitive and functional ability task performance (MCCB, MMAA, PAOFI)
Information on schizophrenia, cognitive impairments and methods to improve cognition
Description of the cognitive training program, including principles and mechanisms
Participant ratings (1-10) of importance of cognitive training and confidence in ability to learn, to assess motivation and promote change talk
Ending interview 1 (summary, perceived impact, readiness for change)
MI Session 2 (~45-60 min)
Summary of previous session's content, emphasizing motivation to change (i.e. improve cognition)
Hands-on demonstration of cognitive training program
Constructing a decisional balance for participating in cognitive training, collaboratively problem-solving potential obstacles; filling out checklist to select reasons participants may want to do cognitive training
Filling out and discussing the patient's change plan (as pertains to cognition), highlighting cognitive training goals, identifying and collaboratively problem solving around obstacles, and eliciting level of commitment for change (i.e. improving cognition)
Ending interview 2 (summary of decisional balance and change plan)
Monthly MI Boosters (~ 20-30 min each)
Open-ended discussion of participant's views of how the training is progressing (whether helpful, perceived barriers, perceived progress, etc.)
Personal feedback on cognitive training task progress since last assessment
Participant ratings (1-10) of importance of continuing cognitive training and confidence in ability to learn (to assess motivation and promote change talk)
Constructing a decisional balance for participating in cognitive training, collaboratively problem-solving potential obstacles; filling out checklist to select reasons participants may want to continue to attend cognitive training
Ending MI Booster (summary, readiness to change/continue training, decisional balance, change plan)

Table 2. CI Intervention Elements

CONTROL INTERVIEW (CI) SESSIONS
Note: throughout both CI sessions, interviewer presents self as expert providing feedback to participant; interviewer avoids open-ended questions, affirmations, reflections, summaries, expressing empathy, etc.
CI Session 1 (~45-60 min)
Opening remarks, focus of sessions on finding out how the participant best learns new information
Completing learning style questionnaires (Achievement Motivation Profile)
Ending interview 1 (participant informed that s/he will receive feedback on learning styles during 2nd interview session)
CI Session 2 (~45-60 min)
Opening remarks (explanation of information provided by learning style questionnaires and how it may be helpful)
Personal feedback on learning styles inventories (Achievement Motivation Profile)
Description of the cognitive training program, including principles and mechanisms
Hands-on demonstration of cognitive rehabilitation program
Ending interview 2 (summary of learning styles and opportunity for questions)
Monthly Sham CI Boosters (~ 20-30 min each)
Review of individual training exercises, soliciting participant opinion of whether they like or do not like specific tasks and how they might change the training
Interventionist provides rationale for presence/types of training tasks included and current training structure (emphasis on why current training should not be modified)

Data Analysis for primary aim:

Treatment adherence. Differences between MI and CI conditions on the total number of sessions attended over the 4 month cognitive rehabilitation (CR) phase were compared using Wilcoxon rank-sum test. As the total number of sessions attended followed a Poisson distribution, and as a considerable portion of the participants did not attend any sessions, zero-inflated Poisson (ZIP) model was built to evaluate treatment adherence, with the probability of not attending any sessions based on results of a logistic regression, and the number of sessions attended between conditions based on results of a Poisson regression.

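### Should the comparison of sessions attended have been adjusted for baseline cognition and functional ability?

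*Combined protocol and SAP*

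**What the plan says.** The Study Protocol section sets the outcome: "Primary outcome is cognitive rehabilitation treatment adherence". On size it says "Approximately 120 individuals with psychotic spectrum diagnoses will be recruited", with 1:1 allocation and up to 50 training sessions over four months.

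Under Data Analysis for primary aim, differences between the motivational interview (MI) and control interview (CI) arms in the "total number of sessions attended over the 4 month cognitive rehabilitation (CR) phase were compared using Wilcoxon rank-sum test". A ZIP model follows, with "the probability of not attending any sessions based on results of a logistic regression" and a Poisson regression comparing the number of sessions between arms. No baseline covariate is named for either part.

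On baseline data, the Study Protocol section says: "Following written informed consent and baseline assessment, they will be randomized (1:1) into one of two conditions". It adds: "An additional assessment of cognition and functional capacity will be conducted at the midpoint (end of 2 months) of the cognitive training". At the end of training, "participants will once again undergo comprehensive assessments". Table 1 lists, for the first MI session, "Personal feedback on neurocognitive and functional ability task performance (MCCB, MMAA, PAOFI"). The only stated role for baseline variables is as possible moderators of the MI effect.

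**The concern.** A rank-sum test takes no covariate, and the ZIP description mentions none. Yet pre-randomisation scores on cognition (MCCB) and functional ability (MMAA) seem to exist for both arms: assessment comes before allocation, the midpoint measurement is described as an extra one, the final battery is a repeat, and results are fed back in the first MI session. Adjusting a randomised comparison for prognostic baseline scores is good practice and can raise power at almost no cost. With about 60 per arm, power for a moderate difference could be modest. If so, the trial might miss a real effect on its primary outcome while holding data that could have sharpened the comparison.

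**Working it through.** **1. Inputs.** From the documents: about 120 participants at 1:1, so 120/2 = 60 per arm; sessions from 0 to 50; baseline assessment before randomisation. The documents give no alpha, power, effect size, SD, share with zero sessions, or correlation of baseline scores with attendance. There is therefore no design figure to reproduce, and every size below rests on assumptions.

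**2. Validity.** Randomisation makes the arms comparable without adjustment. In two simulations with different data-generating models, type I error at a nominal two-sided 5% was 4.8% to 5.4% and 4.9% to 5.3% for the Wilcoxon test, and 5.0% to 5.5% and 4.9% to 5.5% for rank ANCOVA. The question is one of efficiency only.

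**3. Possible gain by formula.** Adjustment multiplies the residual variance by (1 − R²), so

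power = Φ( d / √[(1 − R²) × 2/60] − 1.96 ).

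Take d = 0.511, which gives 80% unadjusted power, since 0.511/√(2/60) = 2.80 and Φ(2.80 − 1.96) = 80%. Then:

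- R² = 0.01: 80.4%
- R² = 0.05: 2.80/√0.95 = 2.87, giving 82.0%
- R² = 0.10: 2.80/√0.90 = 2.95, giving 84.0%
- R² = 0.20: 2.80/√0.80 = 3.13, giving 87.9%

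**4. Possible gain by simulation.** Assumed: 60 per arm, 25% zeros in the control arm, two covariates correlated 0.5, a latent shift, 20,000 replicates. The standard error of each power difference is at most 0.3 points.

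| R | Wilcoxon, 0.5 SD | Rank ANCOVA, 0.5 SD | Change (points) | Change at 0.4 SD (points) |
|---|---|---|---|---|
| 0 | 74.7% | 73.9% | −0.8 | −0.5 |
| 0.1 | 74.7% | 74.5% | −0.2 | −0.3 |
| 0.2 | 74.6% | 75.5% | +0.9 | +0.9 |
| 0.3 | 74.4% | 77.4% | +3.0 | +2.5 |
| 0.45 | 74.6% | 82.5% | +7.9 | +8.1 |

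The second simulation used zero-inflated, overdispersed counts with about 30% control zeros and 3,000 runs per setting. Wilcoxon against rank ANCOVA gave 72.1% against 71.2% with unrelated covariates, 69.0% against 71.0% at a fitted rank R² of about 0.06, 61.4% against 69.2% at about 0.18, and 52.2% against 65.8% at about 0.31. The fitted R² includes chance fit of about 2/119 = 0.017.

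The approaches agree: roughly nothing, or a slight loss, for weak covariates, and a useful gain only from about R = 0.3 (R² = 0.09). Nothing in the documents says that cognition or functional ability predicts attendance, so they do not show where in this range the trial lies.

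**5. Missing scores.** The figures in step 4 assume complete covariates. At R = 0.3, power of 77.4% corresponds to a noncentrality of 0.752 + 1.960 = 2.712. A complete-case analysis with 5% missing gives 2.712 × √0.95 = 2.643, power 75.3%. With 10% missing it gives 2.712 × √0.90 = 2.573, power 73.0%, which is below the 74.4% of the unadjusted test on everyone. The missing fractions are assumed and may be lower, since assessment precedes randomisation.

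**6. What adjustment could change now.** The analysis paragraph is in the past tense and describes how attendance was distributed and that a sizeable share attended no sessions. Attendance had apparently been seen. Covariates chosen at that stage belong in a supporting analysis, with the Wilcoxon test and the unadjusted ZIP model left as they are. The power of those planned analyses then stays as it was.

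**7. The ZIP model.** No adjusted ZIP model was simulated, so no gain is shown for it. Adjusted odds ratios also answer a conditional question. In a proportional-odds check at R = 0.45, adjustment moved the median log odds ratio from 0.839 to 0.966 while its standard error rose from 0.330 to 0.341.

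**The case for a change.** The strongest case for the concern is that its facts are right and the remedy is cheap. The Wilcoxon test is unadjusted, the ZIP text names no covariate, and scores taken before randomisation cannot be affected by the intervention. Planned moderator analyses do not replace adjustment, because they ask whether the effect varies and do not sharpen its main estimate. The worst simulated loss is under 1 point, while the gain could reach about 8 points at R = 0.45, or 13.6 points (65.8% less 52.2%) at a fitted R² of about 0.31. Had the adjusted test been fixed as the lead analysis before any outcome was seen, it would have been a defensible choice.

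The facts stand, and so does the remark about design-stage choice. But a defensible alternative does not make the chosen valid method an error, and the larger gains need correlations for which the documents offer no support. The availability of the covariates is also inferred: the baseline battery is not itemised, the instruments are named only in the MI table, and the study schematic is not shown in the text available.

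One part needs no assumption. A sentence saying whether the ZIP model contained baseline covariates would tell the reader whether its odds and rate ratios are conditional on them. That is a reporting detail, and it does not support a claim of lost power.

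**Conclusion.** The concern does not hold. The planned comparison is valid, the passages do not contradict each other, and no stated figure fails. The possible benefit of adjustment runs from a loss of 0.8 points to a gain of 7.9 points of power for R from 0 to 0.45, assuming 60 per arm, a 0.5 SD latent shift, 25% control zeros and complete baseline scores. It reaches 3 points only at about R = 0.3. An adjusted model added after attendance was known would not strengthen the planned test or change its conclusion. Leaving out baseline covariates is an acceptable choice of analysis here, and preferring an adjusted one is a matter of taste.

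### The single primary adherence outcome goes through a Wilcoxon test and a two-part ZIP model with no deciding result named, and the Poisson part has no stated safeguard against overdispersion

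*Combined protocol and SAP*

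**What the plan says.** The Study Protocol section of the combined protocol and SAP names one primary outcome: "Primary outcome is cognitive rehabilitation treatment adherence". It plans 1:1 randomisation to MI or CI, up to 50 training sessions over 4 months, and a sample described as "Approximately 120 individuals with psychotic spectrum diagnoses will be recruited".

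The only analysis text is one paragraph under the heading on data analysis for the primary aim. It contains two analyses of session totals:

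- MI and CI totals over the training "phase were compared using Wilcoxon rank-sum test".
- A "zero-inflated Poisson (ZIP) model was built to evaluate treatment adherence". Its zero part is described as "with the probability of not attending any sessions based on results of a logistic regression", and its count part as "the number of sessions attended between conditions based on results of a Poisson regression".

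Two reasons are given for ZIP: "As the total number of sessions attended followed a Poisson distribution", and "a considerable portion of the participants did not attend any sessions".

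Neither analysis is labelled primary or supportive. The document gives no alpha, sidedness, hierarchy, multiplicity rule or dispersion check. The paragraph is complete and carries no sign of removed text.

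**The concern.** Two MI/CI comparisons of one primary outcome are written: the Wilcoxon test and the Poisson part. The logistic part is described without mention of condition, so a third comparison is possible but not written. With no deciding result, a reader cannot tell what counts as success when the results disagree.

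The second problem is independent of the first. A Poisson regression with model-based standard errors assumes that the variance equals the mean among attenders. Attendance over four months often varies between people by more than that, and the text describes no check. If it does, the Poisson part rejects too often even as the only named test.

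The stated reasons for ZIP are also observed features of the outcome, reported in the past tense. That leaves open when the model was specified.

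**Working it through.** The plan gives no alpha, power or error rate, so there is no figure of its own to reproduce.

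**Inputs from the document.** About 120 participants at 1:1, hence 120/2 = 60 per arm; counts capped at 50.

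**Assumed inputs.** Two-sided 0.05 per test; 10–50% with zero sessions; attender mean 15 or 25; attender counts Poisson, or gamma-Poisson with nominal variance/mean 2, 4 or 8.

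**Step 1: can the total be Poisson?** A plain Poisson with mean 15 gives a zero share of exp(−15), about 0.00003%. With zero share z and Poisson attenders of mean m, the overall variance/mean is 1 + z·m. This runs from 1 + 0.10 × 15 = 2.5 to 1 + 0.50 × 25 = 13.5. The Poisson statement can therefore hold only for attenders.

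**Step 2: bound for two comparisons.** If they were independent, 1 − 0.95² = 9.75%. They share data, so simulation is needed.

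**Step 3: null simulation.** There were 20,000 trials in each of 40 settings, using a tie-corrected Wilcoxon and a Wald test of the zero-truncated Poisson rate among attenders. Monte Carlo standard error was at most 0.35 points. Percentages of null trials rejecting:

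| Attender variance/mean | Wilcoxon alone | Poisson part alone | Either of the two |
|---|---|---|---|
| 1 (Poisson) | 4.8–5.2 | 4.5–5.2 | 7.7–9.5 |
| 2 | 4.6–5.3 | 16.3–16.9 | 17.6–20.4 |
| 4 | 4.6–5.3 | 30.9–33.1 | 31.7–35.4 |
| 8 | 4.6–5.3 | 43.8–47.3 | 44.1–49.2 |

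The Wilcoxon range in the last three rows is pooled over them. A separate simulation with attender means of 10, 20 and 30 gave 7.4–9.7% for either comparison under Poisson counts, hence about 7–10% overall. A condition term in the logistic part would raise any-of-three to 9.9–11.7%.

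**Step 4: hand check of the Poisson column.** If the true variance is φ times the model variance, the size is 2[1 − Φ(1.96/√φ)].

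- φ = 2: 1.96/1.414 = 1.386, giving 16.6%.
- φ = 4: 1.96/2 = 0.98, giving 32.7%.
- Nominal 8: the cap at 50 lowers the realised ratio to 6.4–7.4, giving 43.8% (1.96/2.530 = 0.775) to 47.1% (1.96/2.720 = 0.721).

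These agree with the simulation.

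**Step 5: the misleading direction.** The Poisson part is significant while the Wilcoxon is null in 2.6–4.6% of null trials if attenders are Poisson, and in 12.6–44.3% at variance/mean 2–8. Those rates count both directions. Counting only results that favour MI gives about half: 1.2–2.2% and 6.2–21.6%.

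**Step 6: remedies.** With robust errors, the Poisson part rejects in 5.1–6.1% across all 40 settings. A joint two-degree-of-freedom ZIP test rejects in 12.0–42.4% at variance/mean 2–8 with model-based errors, and in 3.7–5.8% with robust errors.

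**The case against.** The strongest reply is that ordinary readings already give one main analysis. The Wilcoxon comes first and is the only stated comparison of the total itself. Alternatively, ZIP is the model said to evaluate adherence, which is the name of the primary outcome. Both readings are reasonable, but the text does not choose between them. If ZIP is meant, it still has two parts and no rule for combining them.

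Several replies stand and limit the point:

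- A reader might infer that the trial's error rate is 7–10%. The documents do not support that: the figure needs a rule that either result counts, which is neither stated nor excluded.
- A reader might attribute the 16–47% to the missing hierarchy. It comes from assumed overdispersion and would remain if the Poisson part were the only named test. The document gives no dispersion figure.
- A reader might infer that ZIP was certainly chosen after the data were seen. The past tense in a document dated 09/01/2021 suggests this, but an earlier dated plan may exist. The effect of such a choice has not been quantified.
- The Poisson statement is partly loose wording. Its natural sense is Poisson apart from the zeros, and that is the sense tested here.
- Making the Wilcoxon decisive has a power cost, set out with the fix.

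**Conclusion.** The point holds as two separate defects in the analysis text.

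The missing deciding result is a fact of the document and rests on no assumption. Its numerical size is illustrative: about 7–10% false differences if either written comparison counts, with about 1–2% of null trials giving a Poisson part that favours MI beside a null Wilcoxon. Both figures take attenders as Poisson, two-sided 0.05 per test, 60 per arm and 10–50% zeros; only the arm size follows from the document.

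The unprotected Poisson part could matter more, but how much depends on dispersion that the document does not report. At variance/mean 2–8 it rejects in about 16–47% of null trials, and about 6–22% of null trials give an MI-favouring result with a null Wilcoxon. If attenders are truly Poisson, this second defect vanishes.

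Whether the trial's actual results conflict cannot be known from these pages. This should be corrected. It does not show that the trial's conclusion is wrong.

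**What to change.** - Name one deciding result at two-sided 0.05 and call the rest supportive. If an earlier dated plan names one, that one stands. Otherwise the Wilcoxon on session totals in all randomised participants, zeros included, is the simplest choice, and it held about 5% at every dispersion tried. A joint two-degree-of-freedom ZIP test with robust errors is an acceptable alternative.
- Fit ZIP with a dispersion check and robust standard errors, or use a zero-inflated negative binomial model. State whether the logistic part carries a condition term.
- Give the date on which each analysis was specified. If the deciding test is named after the outcome was seen, say so, because naming it then does not restore the 5% rate.

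The work is SAP wording, a dated disclosure and a refit. There are two downsides. A significant ZIP part alone can no longer be called a positive primary result. The Wilcoxon also has less power for an effect confined to attenders: for 20 versus 23 sessions with Poisson attenders and 60 per arm (assumed), it has about 38% at 30% zeros and 14% at 50% zeros. The Poisson part has about 84% and 70%, and the joint ZIP test with model-based errors 76% and 60%. For an effect only on non-attendance (40% versus 25% zeros, assumed), the Wilcoxon and the joint test are similar, at 31% and 32%.

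### The ZIP count part takes its p-value and interval from an unchecked Poisson variance; both are too optimistic if attenders vary more than Poisson

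*Combined protocol and SAP*

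**What the plan says.** The Study Protocol section states "Primary outcome is cognitive rehabilitation treatment adherence" and sets the range of the outcome: "All participants will be invited to participate in 4 months (up to 50 sessions) of computerized cognitive rehabilitation training". Session totals therefore run from 0 to 50.

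The analysis text is the single paragraph on treatment adherence under Data Analysis for primary aim. It names two analyses:

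- Session totals in the two arms "were compared using Wilcoxon rank-sum test".
- A ZIP model is fitted, on this reasoning: "As the total number of sessions attended followed a Poisson distribution, and as a considerable portion of the participants did not attend any sessions". Non-attendance comes from a logistic part, and "the number of sessions attended between conditions based on results of a Poisson regression".

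The paragraph does not say which analysis decides the primary aim. It reports no mean, variance or zero share, and no check of fit. It mentions neither a robust or scaled variance nor a model that allows extra spread.

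**The concern.** A Poisson regression derives its standard error from the assumption that variance equals mean. The inflation component removes the excess zeros from that calculation. It does nothing about spread among people who attend at least once.

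Each participant contributes one total over 4 months. For such totals to be Poisson among attenders, everyone in an arm would have to share one attendance rate. Early stopping or stable differences between people breaks this and makes the standard error too small. Near-complete attendance against the 50-session ceiling does the opposite.

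The count part is the only described source of an effect size and interval for how many sessions MI adds among attenders. The Wilcoxon test gives neither. If the variance is wrong, the session-rate ratio carries a misleading p-value and confidence interval on the primary outcome.

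**Working it through.** **Inputs from the documents.** "Approximately 120 individuals with psychotic spectrum diagnoses will be recruited", and "they will be randomized (1:1) into one of two conditions", so 60 per arm; totals from 0 to 50. The plan has no figure to reproduce.

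**Assumptions (not in the documents).** Two-sided 0.05; no MI effect; 25% zeros in each arm; a range of values for φ, the variance/mean ratio among attenders.

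**Step 1: does the stated Poisson fit settle it?** A Poisson total has P(0) = exp(−mean): 5.0% at mean 3, 0.67% at mean 5, 0.0045% at mean 10. A considerable share of zeros is incompatible with a Poisson total at any sizeable mean. If the statement was meant for attenders only, no variance among them is given to support it.

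**Step 2: size of the error.** If variance = φ × mean, the true standard error is √φ times the Poisson one, so

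type I error = 2[1 − Φ(1.96/√φ)].

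- φ = 0.5: 0.6%
- φ = 1: 5.0%
- φ = 1.5: 1.96/1.22 = 1.60, giving 11.0%
- φ = 2: 1.96/1.41 = 1.39, giving 16.6%
- φ = 5: 38.1%
- φ = 10: 1.96/3.16 = 0.62, giving 53.5%

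**Step 3: which φ can a 0–50 count produce?**

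- Beta-binomial with mean proportion p and within-person correlation ρ: φ = (1 − p)(1 + 49ρ). At p = 0.5, ρ = 0 gives 0.5, 0.04 gives 1.5, 0.09 gives 2.7 and 0.20 gives 5.4. The Poisson variance is right only at ρ = 1/49, about 0.02.
- Binomial(50, 0.8), everyone attending alike: φ = 0.2.
- Uniform on 1–50: mean 25.5, variance (50² − 1)/12 = 208.25, φ = 8.2.
- Binomial(50, 0.8) (mean 40, variance 8), with a share q stopping after 1–12 sessions, taken as uniform (mean 6.5, variance 11.9). At q = 0.10 the mean is 36.65, the variance is 0.9×8 + 0.1×11.9 + 0.09×33.5² = 109.4, and φ = 3.0. The same sum gives 1.6 at q = 0.05 and 5.7 at q = 0.20.

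**Step 4: simulation under no effect.** 20,000 trials per scenario. Each arm's count mean was estimated by zero-truncated Poisson maximum likelihood, which is the ZIP count estimate when arm enters both parts. The log rate ratio was tested with the model-based standard error.

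| Attenders | φ | True SD / model SE | Type I error |
|---|---|---|---|
| Binomial(50, 0.8) | 0.2 | 0.45 | 0.0% |
| Binomial(50, 0.5) | 0.5 | 0.71 | 0.6% |
| Poisson(25) | 1.0 | 0.99 | 4.9% |
| Beta-binomial, ρ 0.04 | 1.5 | 1.21 | 10.5% |
| Beta-binomial, ρ 0.09 | 2.7 | 1.65 | 23% |
| Beta-binomial, ρ 0.20 | 5.4 | 2.33 | 40% |
| Uniform 1–50 | 8.2 | 2.87 | 50% |

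With 5%, 10% and 20% early stoppers the error is about 12%, 25% and 41%. A beta-binomial with mean 15 and ρ 0.33 (φ = 10.3 among attenders) gave 52% to 54% in smaller runs of 2,000. Coverage of the 95% interval is about 77% at φ = 2.7 and 50% at φ = 8.2. Zero shares of 15% and 40% move the count-part figures by less than 1 point.

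**Step 5: the same data with other tests.** In the 20,000-trial scenarios a sandwich standard error on the same estimate gave 4.0% to 5.4%. The Wilcoxon test on all totals (4,000 trials each) gave 4.3% to 5.5%.

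**Step 6: full ZIP fits.** 300 null trials each, model-based then sandwich: Binomial(50, 0.8), 0.0% and 4.0%; beta-binomial with ρ 0.10, 22.7% and 7.0%; 10% early stoppers, 26.3% and 3.3%; uniform, 46.7% and 5.3%. The Monte Carlo error at 5% is 1.3 points, so these agree with Step 4.

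**The case against.** - **No overdispersion is shown.** Nothing in the documents anchors φ, and the results run from 0% to 54%. The plain test could be conservative, correct or badly anti-conservative. This stands: the claim is about an unprotected assumption, not a demonstrated error.
- **The first-listed analysis is valid.** The Wilcoxon test does not use the Poisson variance. This also stands, and it limits the harm to the session-rate ratio, its p-value and its interval. But the plan does not rank the two analyses, and it presents the ZIP model as its means of evaluating adherence.
- **Silence is not proof of omission.** The paragraph is a short summary in the past tense, so dispersion may have been examined without being described. That is possible; the reader still cannot tell.
- **The Poisson statement may mean Poisson apart from the excess zeros.** That is a fair reading, and it is exactly the assumption for which no evidence is reported.
- **The sandwich remedy is not perfect everywhere.** A wider set of scenarios with means of 15 to 35 sessions gave up to 6.6%. At a mean of about 5 sessions it gave 5.6% to 6.7%, and the fitted structural-zero share drifted from 25% to between 37% and 50%. This is a minor limit on the fix and leaves the main point intact.

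**Conclusion.** The concern holds, as a conditional one that should be fixed. The between-arm comparison of session counts rests on a Poisson variance that is asserted, with no check or protection described. If φ among attenders lies between 1.5 and 10, the standard error is too small by a factor of about 1.2 to 3.2 (√1.5 to √10). The nominal 5% test then rejects about 11% to 54% of the time under no effect. As few as 5% early stoppers among otherwise uniformly high attenders is enough to more than double the error. If φ is below 1, the intervals are too wide and the test loses power.

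These sizes rest on the assumed level, zero share and attendance patterns listed in the working. The claim that no safeguard is described rests on the documents alone.

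**What to change.** Keep the Wilcoxon test, the logistic part and the ZIP point estimates. Then:

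1. Report the mean, variance and variance/mean ratio among attenders, by arm.
2. Base the count-part p-value and confidence interval on sandwich or bootstrap standard errors. This corrects the error in either direction.
3. Add a zero-inflated negative binomial model, or a beta-binomial with maximum 50, as a sensitivity analysis. This matters most if mean attendance turns out to be low, where the sandwich test is slightly liberal and the ZIP zero share is less reliable.
4. Replace the statement that totals were Poisson with one saying that attendance is a count from 0 to 50 with excess zeros, and give the observed dispersion.

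The cost is one option in the model call, a few descriptive statistics, one sensitivity fit and a sentence of wording. No new data are needed. The downside is that intervals will usually be wider; if attenders really are Poisson, almost nothing changes.
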